7.1.2. PET Scan Parameters

7.1.2.1. Deriving PET Scan Parameters

• The PET Scan parameters will be compiled into csv files as per specifications agreed in the External Data Vendor Agreement and will be transmitted to GSK via the External Alliance Portal

Table 4 Derived PET Scan Parameters

Parameter	Parameter Description
SUV Mean	Ratio of tissue mean radioactivity concentration, averaged over a larger RoI, at a
	point in time C(T) and the injected dose of radioactivity per kilogram of the
	patient's body weight for larger regions of interest(>=3 cm):
	SUV = C(T)/[injection dose (MBq)/patient's weight (kg)]
SUV Peak	Ratio of tissue radioactivity concentration, averaged over a small sphere of defined
1 out	diameter (typically 10 mm) at a point in time C(T) and the injected dose of
	radioactivity per kilogram of the patient's body weight for smaller regions of
	interest:
	SUV = C(T)/[injection dose (MBq)/patient's weight (kg)]
SUV max	Ratio of maximum tissue radioactivity signal at a point in time C(T) and the
	injected dose of radioactivity per kilogram of the patient's body weight for larger
	regions of interest(>=3 cm):
	SUV = C(T)/[injection dose (MBq)/patient's weight (kg)]

Parameter	Parameter Description
Activity	Tissue mean radioactivity in Bq/ml from the RoI used for SUVmean
Conc.	
Mean	
Total	The total amount of radioactivity in MBq or Bq contained within ROI at time (T).
Activity	This corresponds to the total organ radioactivity if ROI corresponds to the total
	tissue volume.
ROI	The volume of the ROI used in measurements
Volume	
Percent	The percent of Injected dose found within ROI at time (T)
Injected	
Dose	
Organ	The amount of radiation delivered to a particular organ
Doses	
Effective	The tissue-weighted sum of the organ doses in all specified tissues and organs of
Dose	the human body

7.1.2.2. Statistical Analysis of PET Scan Parameters

All derived PET Scan Imaging parameters will be summarized where appropriate, (i.e. n, arithmetic mean, standard deviation, minimum, median and maximum) over time. Graphical displays will also be produced over time for applicable PET-CT imaging endpoints.

Listings will be produced for all the collected data.

8. SECONDARY STATISTICAL ANALYSES

8.1. Pharmacokinetic Analyses

8.1.1. Overview of Planned Pharmacokinetic Analyses

The pharmacokinetic (PK) analyses will be based on the PK population, unless otherwise specified.

Table 5 provides an overview of the planned analyses, with full details being presented in Appendix 8: List of Data Displays.

[Endpoint /	Untransformed				Log-Transformed									
Parameter/ Display	Stat	s Ana	lysis	Sum	mary	Indiv	idual	Stat	s Ana	lysis	Sum	mary	Indiv	idual
Туре]	Т	F	L	Т	F	F	L	Т	F	L	Т	F	F	L
PK Concentration														
Whole blood					Y ^[1]	Y ^[1]	Y							
concentration of ⁸⁹ Zr- GSK3128349				Y										
Plasma Concentration of ⁸⁹ Zr-GSK3128349				Y	Y ^[1]	Y ^[1]	Y							
Plasma concentration of GSK3128349				Y	Y ^[1]	Y ^[1]	Y							
Urine Concentration of ⁸⁹ Zr-GSK3128349				Y	Y ^[1]	Y ^[1]	Y							
PK Parameters														
Derived PK parameters				Y			Y				Y			
for whole blood														
concentration of ⁸⁹ Zr-														
GSK3128349														
Derived PK parameters				Y			Y				Y			
for plasma														
GSK3128349														
Derived PK parameters				Y			Y				Y			
for plasma														
concentration of														
GSK3128349														

 Table 5
 Overview of Planned Pharmacokinetic Analyses

NOTES :

• T = Table, F = Figure, L = Listings, Y = Display generated.

• Y^[1]= Linear and Semi-Log Plots would be produced

8.1.1.1. Analyses

Whole blood and plasma concentrations time data of 89Zr-GSK3128349 and plasma concentrations time data of GSK3128349 will be analyzed by non-compartmental methods. From the plasma concentration-time data, the following PK parameters may be determined as data permits:

Maximum observed plasma concentration (Cmax), Time to achieve Cmax (Tmax), Apparent terminal phase half-life (t1/2), Area under the concentration-time curve from time zero (predose) to last time of quantifiable concentration within a subject (AUC[0-t]) for 89Zr-GSK3128349 and GSK3128349, Area under the concentration-time curve from time zero (predose) extrapolated to infinite time (AUC[0- ∞]) only for GSK3128349, Clearance and Volume of distribution.

Pharmacokinetic data will be presented in graphical and/or tabular form and will be summarized descriptively. Figures for individual plasma concentrations will be presented on both a linear and semilog scale for ⁸⁹Zr-GSK3128349 and GSK3128349. Linear and semi-log figures for mean and median plasma concentrations versus time for each treatment regimen will also be generated.

For each of the derived PK parameters of ⁸⁹Zr-GSK3128349 and GSK3128349, the following summary statistics will be calculated: n (number of observations), arithmetic mean, standard deviation, median, minimum, maximum, and the 95% confidence interval of arithmetic mean. In addition, summary statistics for log-transformed PK parameters [i.e., AUC(0-t), AUC(0- ∞), Cmax, Clearance, t¹/₂ and Volume], except tmax will include geometric mean, 95% confidence interval of the geometric mean, standard deviation of the logarithmically transformed data, and inter-subject coefficient of variation [CVb (%)].

8.1.2. Drug Concentration Measures

Refer to Appendix 3: Data Display Standards & Handling Conventions (Section 10.3.3 Reporting Process & Standards).

8.2. Safety Analyses

8.2.1. Overview of Planned Adverse Event Analyses

The safety analyses will be based on the Safety population, unless otherwise specified. This section will be completed in the final RAP.

Table 7 provides an overview of the planned analyses, with further details of data displays being presented in Appendix 8: List of Data Displays.

Table 7	Overview of Planned Adverse Event Analyses

Endpoint / Parameter/ Display Type	Absolute					
	Sun	nmary	Individual			
	Т	F	L			
Adverse Events (AEs)						
All AEs by System Organ Class	Y		Y			
All Drug-Related AEs by System Organ Class	Y		Y			
Subject Numbers for Individual AEs			Y			
Relationship Between AE SOCs, PT & Verbatim Text			Y			
Serious and Other Significant AEs						
Serious AEs by System Organ Class	Y		Y			
Reasons for Considering as a Serious AE			Y			
AEs Leading to Withdrawal from Study	Y		Y			

NOTES:

• T = Table, F = Figures, L = Listings, Y = Yes display generated, SOC = System Organ Class, PT = Preferred Term.

8.2.2. Overview of Planned Clinical Laboratory Analyses

The safety analyses will be based on the Safety population, unless otherwise specified.

Table 8 provides an overview of the planned analyses, with further details of data displays being presented in Appendix 8: List of Data Displays.

Table 8 Overview of Planned Clinical Laboratory Analyses

Endpoint / Parameter/ Display Type		Abs	olute	Change from BL			
	Sum	mary	Individual	Sumr	nary	ary Individual	
	Т	F	L	Т	F	L	
Chemistry							
Clinical Chemistry Parameters	Y			Y			
Chemistry Data for Subjects with Abnormalities of Potential Clinical Concern			Y				
Chemistry Data Abnormalities of Potential Clinical Importance			Y				
Hematology							
Hematology Parameters	Y			Y			
Hematology Data for Subjects with Abnormalities of Potential Clinical Concern			Y				
Hematology Data Abnormalities of Potential Clinical Importance			Y				
Urinalysis							
Urine Concentration Data	Y		Y	Y			

8.2.3. Overview of Planned Other Safety Analyses

The safety analyses will be based on the Safety population, unless otherwise specified.

Table 9 provides an overview of the planned analyses, with further details of data displays being presented in Appendix 8: List of Data Displays.

Table 9	Overview of Planned	Other Safety	y Analyses
---------	---------------------	--------------	------------

Endpoint / Parameter/ Display Type		Absolute			Change from BL			
	Sum	mary	Individual	Sumr	nary	y Individual		
	Т	F	L	Т	F	L		
ECG								
ECG Findings	Υ							
ECG Values by Visit	Υ			Y				
All ECG Values for Subjects with a Value of PCI			Y					
ECG Values of PCI			Y					
Abnormal ECG Findings			Y					
Vital Signs								
Vital Signs by Visit	Υ			Y				
All Vital Signs for Subjects with Values of PCI			Y					
Vital Signs Values of PCI			Y					

9. **REFERENCES**

GlaxoSmithKline Document Number 2014N202021_00 Study ID RES117169 An open label positron emission tomography (PET) imaging study using 89Zirconium labelled GSK3128349 to investigate the biodistribution and clearance of an albumin binding domain antibody (AlbudAb) GSK3128349 following single dose intravenous administration in healthy male subjects.MAY/2016

10. APPENDICES

Section	Appendix
RAP Section 4	: Analysis Populations
Section 10.1	Appendix 1: Protocol Deviation Management
RAP Section 5	: General Considerations for Data Analyses & Data Handling Conventions
Section 10.2	Appendix 2: Time and Events
Section 10.3	Appendix 3: Data Display Standards & Handling Conventions
	 Study Treatment & Sub-group Display Descriptors
	Baseline Definitions & Derivations
	Reporting Process & Standards
Section 10.4	Appendix 4: Derived and Transformed Data
	General, Study Population & Safety
Section 10.5	Appendix 5: Premature Withdrawals & Handling of Missing Data
	Premature Withdrawals
	Handling of Missing Data
Section 10.6	Appendix 6: Values of Potential Clinical Importance
Other RAP App	endices
Section 10.7	Appendix 7: Abbreviations & Trade Marks
Section 10.8	Appendix 8List of Data Displays
Section 10.9	Appendix 9: Example Mock Shells for Data Displays

10.1. Appendix 1: Protocol Deviation Management

10.1.1. Exclusions from Per Protocol Population

As detailed in Section 4.1, Protocol deviations will be tracked by the study team throughout the conduct of the study in accordance with the Protocol Deviation Management Plan and a listing of important Protocol Deviations will be provided.

A Per Protocol Population is not being defined for this study. However additional exploratory sensitivity summaries may be considered, if there are protocol deviations that may affect the primary PET endpoints. Any additional sensitivity summaries will be documented in the CSR.

10.2. Appendix 2: Time & Events

10.2.1. Protocol Defined Time & Events

Procedures	Screening up to 28 days prior to day 1				
Informed Consent	Х				
Demographics	Х				
Eligibility	Х				
Full Physical Exam	Х				
Medical/Medication/Drug/Alcohol Hx	Х				
12-lead ECG (triplicate)	Х				
Vital Signs	Х				
Urine Drug/Alcohol	Х				
HIV, Hep B and Hep C Screen ¹	Х				
Haem/Chem/Urinalysis Tests/UPCR	Х				
Concomitant Medication Review	Х				
 If test performed within 3 months prior to first dose of study treatment, testing at screening is not required 					

Day of study	Day - 1		Day 1				Day 2	Day 4	Day 6	Day 13±1 day	Day 20± 2 days	Day 31 ±2 days	
Time post dosing		Pre-dose	0	1 hour	3 hours	6 hours	8 hours	24 hours					
Admission to Unit	Х												
Brief Physical Exam	Х							X٩					
Medical/Medication/Drug/Alcohol Hx	Х												
12-lead ECG		Xf		X				Х					
Vital Signs		Х		X				Х					
Urine Drug/Alcohol	Х												
Urinalysis	Х							Xi		Х	X	Х	
Spot Urine Protein/Creatinine ratio	Х							Xe			X		
Haematology								Х				Х	
Clinical chemistry	Х							X		Х	Х	Х	Х
Randomisation	Х												
Immunogenicity Blood Sample		Х											
IV Infusion Dosing			Х										
PET imaging and co-localising CT (first subject) ^a				x		x		х		х			
PET imaging and co-localising CT (second subject) ^a					x		x		x	х			
PET imaging and co-localising CT (subsequent subjects) ^{a, b}			<						•				
PK Blood Sampling for MS		Х		X	X	X	Х	Х	Х	Х	X	Х	Х
PK Blood Sampling for scintillation counting ^h		Х		X	x	x	x	x	x	х	x		
Bladder Void ^c		Х											
Urine Collection ^d			←										

Day of study	Day - 1			D	ay 1			Day 2	Day 4	Day 6	Day 13 ± 1 day	Day 20± 2 days	Day 31 ± 2 days
Time post dosing		Pre-dose	0	1 hour	3 hours	6 hours	8 hours	24 hours					
Adverse Event Review				·	•	•			•	•			,
Concomitant Medication Review		←										>	
Discharge								Х					
Outpatient Visit									X	Х	Х	Х	Х
a. Each PET/CT scan must be preceded by heart rate and blood pressure assessments. b. For subsequent subjects (3rd and beyond) timings of PET scans will be based on data analysis from subjects 1 and 2 and may be carried out anytime between 1 and 10-12 days post injection. A maximum of 4 PET scans will be conducted in each subject. c. Pre-dose urine will not be retained. d. 24 hour urine collection. Total volume will be measured. Part of urine sample will be used for scintillation counting. An aliquot will be utilized for UPCR assessment and another stored for later MS PK analysis if required. Based on data from first 2 subjects, urine may be collected for longer than 24 hrs post dose for subsequent subjects. e. Aliquot from 24 hr collection sample, taken after 24 hr collection is complete. f. Triplicate measurement g. Prior to discharge h. Aliquot from MS PK blood sample							12 days iother						

i. Urine sample to be collected prior to discharge

Note: all time points are relative to start of infusion administration.

10.3. Appendix 3: Data Display Standards & Handling Conventions

10.3.1. Study Treatment & Sub-group Display Descriptors

	Treatment Group Descriptions					
	RandAll NG Data Displays for Reporting					
Code	Description	Description	Order			
A	1 mg of Zirconium labeled GSK3128349	GSK3128349	1			

10.3.2. Baseline Definition & Derivations

10.3.2.1. Baseline Definitions

Parameter	Parameter Study Assessments Considered As Baseline							
	Screening	Day -1	Day 1 (Pre-Dose)	Data Display				
Safety								
Haematology	Х			Screening				
Chemistry	Х	Х		Day -1				
Urinalysis	Х	Х		Day -1				
ECG	Х		Х	Day 1(Pre-Dose) ^[1]				
Vitals	Х		Х	Day 1(Pre-Dose) ^[1]				

NOTES :

[1] Mean of Day 1 (Pre-Dose) values will taken as baseline.

10.3.2.2. Derivations and Handling of Missing Baseline Data

Definition	Reporting Details
Change from Baseline	= Post-Dose Visit Value – Baseline
% Change from Baseline	= 100 x [(Post-Dose Visit Value – Baseline) / Baseline]

NOTES :

 Unless otherwise specified, the baseline definitions specified in Section 10.3.2.1 Baseline Definitions will be used for derivations for endpoints / parameters and indicated on summaries and listings.

• Unless otherwise stated, if baseline data is missing no derivation will be performed and will be set to missing.

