7.1. Time and Events Table

7.1.1. Screening

Procedures	Screening up to 28 days prior to day 1
Informed Consent	Х
Demographics	Х
Eligibility	Х
Full Physical Exam	Х
Medical/Medication/Drug/Alcohol Hx	Х
12-lead ECG (triplicate)	Х
Vital Signs	Х
Urine Drug/Alcohol	Х
HIV, Hep B and Hep C Screen ¹	Х
Haem/Chem/Urinalysis Tests/UPCR	Х
Concomitant Medication Review	Х
1 If test performed within 3 months prior treatment, testing at screening is	

RES117169

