10.8.9. Safety Tables

Safety	Tables				
No.	Population	IDSL / TST ID / Example Shell	Title	Programming Notes	Deliverable [Priority]
Advers	e Events (AEs)				
4.1.	Safety	CP_AE1p	Summary of All Adverse Events by System Organ Class		SAC
4.2.	Safety	CP_AE1p	Summary All Drug-Related Adverse Events by System Organ Class		SAC
Labora	tory: Chemistry	1			
4.3.	Safety	LB1	Summary of Chemistry Data		SAC
4.4.	Safety	LB1	Summary of Chemistry Changes from Baseline		SAC
Labora	tory: Haematol	ogy			
4.5.	Safety	LB1	Summary of Haematology Data		SAC
4.6.	Safety	LB1	Summary of Haematology Changes From Baseline		SAC
Labora	tory: Urinalysis	;			
4.7	Safety	LB1	Summary of Urinalysis Data		SAC
4.8	Safety	LB1	Summary of Urinalysis Changes from Baseline		SAC
ECG					
4.9	Safety	EG1	Summary of ECG Findings		SAC
4.10	Safety	EG2	Summary of ECG values		SAC
4.11	Safety	EG2	Summary of Change from Baseline in ECG Values by Visit		SAC
Vital	Signs				
4.12	Safety	VS1	Summary of Vital Signs		SAC
4.13	Safety	VS1	Summary of Change From Baseline in Vital Signs by Visit		SAC

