10.8.10. ICH Listings

ICH : Lis	CH : Listings							
No.	Population	IDSL / TST ID / Example Shell	Title	e Programming Notes				
Subject	Disposition							
1.	All Screened	ES7	Listing of Reasons for Screen Failure		SAC			
2.	Safety	ES2	Listing of Reasons for Study Withdrawal		SAC			
Protoco	ol Deviations							
3.	Safety	DV2	Listing of Important Protocol Deviations		SAC			
4.	All Screened	IE3	Listing of Subjects with Inclusion/Exclusion Criteria Deviations	ting of Subjects with Inclusion/Exclusion Criteria Deviations				
Populat	ions Analysed							
5.	All Screened	SA3a	Listing of Subjects Excluded from Any Population		SAC			
Demogi	raphic and Bas	eline Characterist	tics					
6.	Safety	DM2	Listing of Demographic Characteristics		SAC			
7.	Safety	DM9	Listing of Race		SAC			
Prior an	d Concomitan	t Medications						
8.	Safety	CP_CM3	Listing of Concomitant Medications		SAC			
Exposu	Exposure and Treatment Compliance							

RES117169

ICH : Li	stings				
No.	Population	IDSL / TST ID / Example Shell	Title	Programming Notes	Deliverable [Priority]
9.	Safety	EX3	Listing of Exposure Data		SAC
Advers	e Events				
10.	Safety	CP_AE8	Listing of All Adverse Events		SAC
11.	Safety	AE7	Listing of Subject Numbers for Individual Adverse Events		SAC
12.	Safety	AE2	Listing of Relationship Between Adverse Event System Organ Classes, Preferred Terms, and Verbatim Text		SAC
Serious	and Other Sig	nificant Adverse	Events		
13.	Safety	CP_AE8	Listing of Serious Adverse Events		SAC
14.	Safety		Listing of Reasons for considering as a Serious Adverse Event		SAC
Chemis	try Data				
15.	Safety	LB5	Listing of All Clinical Chemistry Data for Subjects with Abnormalities of Potential Clinical Importance		SAC
16.	Safety	LB5	Listing of Chemistry Abnormalities of Potential Clinical Importance		SAC
Labora	tory Data				
17.	Safety	LB5	Listing of All Haematology Data for Subjects with Abnormalities of Potential Clinical Importance		SAC
18.	Safety	LB5	Listing of Haematology Abnormalities of Potential Clinical Importance		SAC
ECG					
19.	Safety	CP_EG3	Listing of All ECG Values for Subjects with a Value of Potential Clinical Importance		SAC
20.	Safety	CP_EG3	Listing of ECG Values of Potential Clinical Importance		SAC

RES117169

ICH : Li	CH : Listings						
No.	Population	IDSL / TST ID / Example Shell	Title	Programming Notes	Deliverable [Priority]		
21.	Safety	CP_EG5	Listing of Abnormal ECG Findings		SAC		
Vital S	igns						

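### SAP 10.3.2.2 writes no fallback to Screening, so a subject without the Day -1 or pre-dose value drops out of that parameter's change-from-baseline table

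*SAP*

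**What the plan says.** SAP 10.3.2.2 ties every derivation to the preceding section: "the baseline definitions specified in Section 10.3.2.1 Baseline Definitions will be used for derivations for endpoints / parameters". It then gives the missing-data rule, prefaced by a proviso for anything stated elsewhere: "if baseline data is missing no derivation will be performed and will be set to missing".

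The table in SAP 10.3.2.1, under the heading "Study Assessments Considered As Baseline", ticks Screening for haematology, chemistry, urinalysis, ECG and vital signs. Its Data Display column names one assessment for each: Screening for haematology, Day -1 for chemistry and urinalysis, and Day 1 pre-dose for ECG and vital signs. A note to the last two reads "Mean of Day 1 (Pre-Dose) values will taken as baseline".

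Protocol 7.1.1 schedules "Haem/Chem/Urinalysis Tests/UPCR" at Screening, up to 28 days before Day 1, together with triplicate ECG and vital signs. A second pre-dose value is therefore planned for every parameter whose displayed baseline is Day -1 or Day 1 pre-dose.

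The displays concerned are Table 4.4, "Summary of Chemistry Changes from Baseline", and its counterparts for urinalysis (4.8), ECG (4.11) and vital signs (4.13). Individual chemistry data appear in Listing 15, "Listing of All Clinical Chemistry Data for Subjects with Abnormalities of Potential Clinical Importance", and in Listing 16, which is limited to the abnormal values themselves.

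**The concern.** The rule discards a pre-dose measurement that is planned for every subject and accepts no substitute for it. With so few subjects, each one carries real weight in a descriptive change table.

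The chemistry case matters most. Renal injury is the first risk in Protocol Table 3, and the only renal criterion in SAP 10.6.1 is a change in creatinine from baseline. If the Day -1 value is missing and Screening may not stand in, that criterion cannot be evaluated. Listings 15 and 16 cover only flagged subjects and no full chemistry listing is planned, so his creatinine values would appear in neither unless another analyte flagged him.

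For ECG, Table 4.11 is the only planned display of change, although Protocol 5.4.2 uses a QTc change from baseline as one of its evaluation criteria.

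The Screening ticks add an ambiguity. For chemistry and urinalysis, one programmer could treat Screening as an eligible baseline and another could treat Day -1 as the only one. The two would then produce different tables from the same data.

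**Working it through.** The plan states no figure on this point, so there is none to reproduce.

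**1. Trace the rule by parameter** (SAP 10.3.2.1 and 10.8.9).

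| Parameter | Assessments ticked | Baseline displayed | Change table | Screening value left unused if displayed baseline is missing? |
|---|---|---|---|---|
| Haematology | Screening | Screening | 4.6 | No; Screening is the baseline |
| Chemistry | Screening, Day -1 | Day -1 | 4.4 | Yes |
| Urinalysis | Screening, Day -1 | Day -1 | 4.8 | Yes |
| ECG | Screening, Day 1 pre-dose | Day 1 pre-dose mean | 4.11 | Yes |
| Vital signs | Screening, Day 1 pre-dose | Day 1 pre-dose mean | 4.13 | Yes |

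**2. Look for a fallback elsewhere.** The rule's proviso would allow one. SAP 10.4.1 covers several values at one time point or within one window. SAP 10.5.2 covers blank fields, outliers and partial dates. Neither says what replaces a missing baseline.

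**3. Size of one loss.** With n = 6 to 8 (Protocol 4.1), the share lost is 1/n: 1/6 = 16.7% and 1/8 = 12.5%. This applies to the affected parameter only. With a Screening fallback the table keeps 6 of 6 rather than 5 of 6, or 8 of 8 rather than 7 of 8.

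**4. Chance of at least one loss.** The documents give no missing rate. The values of p below are assumptions: the chance per subject that a given displayed baseline is missing, independent between subjects. The formula is 1 − (1 − p)^n.

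| Assumed p | n = 6 | n = 8 |
|---|---|---|
| 1% | 5.9% | 7.7% |
| 2% | 11.4% | 14.9% |
| 5% | 26.5% | 33.7% |
| 10% | 46.9% | 57.0% |

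**5. The creatinine criterion.** SAP 10.6.1 prints a rise of 44.2 mmol/L. Taking a molar mass of 113.12 g/mol (assumed), 44.2 × 113.12 / 10 ≈ 500 mg/dL. In µmol/L the same number would be about 0.5 mg/dL. For illustration, a rise from 80 to 130 µmol/L is 50 µmol/L, or 0.05 mmol/L. It exceeds 44.2 only if the unit is µmol/L. As printed, the criterion cannot realistically be met by anyone, with or without a baseline. A fallback therefore makes the change derivable but does not by itself give a working flag.

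**6. What survives a missing baseline.** The absolute-value tables (4.3, 4.7, 4.10, 4.12) keep the subject. ECG and vital-sign limits in SAP 10.6.2 and 10.6.3 are absolute, so Listings 19 to 23 still work. Two of the three renal triggers in Protocol 5.4.3 (haematuria; UPCR above 0.5) need no baseline. The third, an eGFR decline, does not name its reference visit.

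**The case against.** The strongest reply is that this is a convention, not an error. The SAP pre-specifies a baseline close to dosing and declines to replace it with a value up to four weeks old. The study is exploratory and tests no hypotheses, and the primary PET analysis is untouched. All of that stands, and it limits the point to an improvement. The age argument is weaker than it looks, because the SAP already accepts Screening as the haematology baseline. In fairness, no later pre-dose haematology is scheduled.

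A second reply is that the loss is unlikely. Subjects are admitted on Day -1, when chemistry and urinalysis are due, and are still in the unit for the pre-dose ECG and vital signs. Protocol section 7 requires adherence to the schedule. That also stands, and it is why the probabilities above are only labelled assumptions.

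A third reply is that the Screening ticks already make Screening an eligible baseline. For chemistry and urinalysis that reading is open. For ECG and vital signs the note on the pre-dose mean closes it. An open reading is itself a reason to write the rule down.

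Three stronger readings are tempting and are not supported:

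- **The subject escapes renal surveillance.** A reader might infer this, but the creatinine criterion is the only renal one in SAP 10.6.1, not in the trial. The haematuria and UPCR triggers remain. Laboratory abnormalities judged clinically significant are adverse events and appear in Listing 10. Listing 15 shows all his chemistry if any other analyte flags him.
- **ECG and vital-sign flags are lost too.** Those limits are absolute. Only the rows of Tables 4.11 and 4.13 are affected.
- **Confidence intervals for mean change widen.** The SAP specifies no such interval for the safety change tables, so no precision loss can be claimed on a planned output.

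**Conclusion.** The point holds as a minor one. No fallback to Screening is written, and on a literal reading a subject without the displayed Day -1 or pre-dose value is lost from one change table per affected parameter. That is 12.5% to 16.7% of the cohort for each subject lost. If the missing value is Day -1 creatinine, the SAP's own renal criterion also cannot be evaluated for him.

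The effect depends on a baseline assessment actually being missed, which the in-unit schedule makes unlikely, and it falls on descriptive safety displays only. For chemistry and urinalysis the conclusion rests on reading the Data Display column as the operative baseline, which the ticked Screening column leaves open. The unit of the creatinine limit is a separate and larger weakness of that criterion.

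**What to change.** Amend the note in SAP 10.3.2.2 to: *If the baseline displayed in 10.3.2.1 is missing, the last non-missing pre-dose value (Screening) is used and footnoted; change is set to missing only if no pre-dose value exists.* This settles both readings of the Screening ticks.

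Correct the unit printed for the creatinine limit in SAP 10.6.1 at the same time, because the fallback cannot make that criterion work without it.

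The cost is one sentence, one line of derivation code and a footnote on the affected tables. The downside is a reference value up to 28 days old for that subject, which the footnote discloses.
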